## 6 STUDY TIMETABLE

### 6.1 Timeline

December 2016 through April 2018 will be used for preparing and finalizing protocol, source documents and preparing submission for the IRB.

During this time, we will also:

- create the real time read group
- create training plan
- finalize DSMB members

### 6.2 Data Collection Period

April 2018- April 2019 will begin screening and recruitment. PI will travel to sites to ensure consistency with using source documents, data base entry and reading results from PillCam

### 6.3 Final Analysis

April 2019-November 2019 will be for data cleaning, data analysis and manuscript preparation and submittal.

## **7 STUDY PROCEDURES**

### **7.1 Screening and Randomization**

Potential study subjects will be identified while present in the Emergency Department. While the patient is in the ED, a member of the research team will be notified. This researcher will determine if the patient meets the inclusion and exclusion criteria. If the patient meets enrollment criteria, the study protocol will be explained to the patient. If they express interest in participation, informed consent will be obtained, randomization will take place, study procedures followed, and follow-up with GI for EGD will be arranged before the patient is discharged from the ED.

### **7.2 Procedural Treatment Protocol**

### **7.3 Study Outcomes**

#### ***7.3.1 Primary Outcomes***

Our primary goal is to test whether ED Video Capsule Endoscopy (VCE) is able to safely discharge low risk patients for outpatient evaluation and management.

#### ***7.3.2 Secondary Outcomes***

Our secondary objective is to estimate the sensitivity and specificity of VCE compared to subsequent EGD in the detection of serious bleeding lesions in the upper gastrointestinal (GI) tract.

### **7.4 Baseline Procedures**

In this randomized clinical trial, the following data and procedures will be performed at screening:

- Informed consent
- Eligibility
- Medical history
- Physical exam
- Medications
- Labs

### **7.5 Patient Management and Follow-up**

After randomization, patients are contacted on days 7 and 30. All the interventions and clinical follow-up in this study are those normally performed in the treatment of patients diagnosed with Upper GI Bleed. The only treatments that are not routine are the VCE PillCam event, read and subsequent discharge to home. Follow-up data will be collected in one of three ways: telephone follow-up is the most preferred method, but email communication or texting to the patient's cell-phone can also be used, in the case that a telephone call is not feasible.

## 7.6 Adverse Event Reporting

Detailed information concerning adverse events will be collected and evaluated throughout the conduct of the protocol. Results of clinical observations, laboratory tests, and reported events form the basis for evaluating the safety profile of this therapy. At all contacts, patients will be questioned regarding side effects or symptoms associated with the study medication which are as follows:

- Difficulty swallowing the PillCam UGI
- Capsule stuck in the stomach or bowel
- Inability to pass PillCam naturally through a bowel movement
- Surgical intervention
- Aspiration
- Possible skin irritation from the sensors

The clinical center will report adverse events to the coordinating center in a timely fashion. The coordinating center will summarize and report adverse events to the DSMB.

Additional procedures are warranted for cases of serious adverse events which is defined by the FDA as a patient outcome that is: (1) death; (2) life-threatening, i.e., the patient was at substantial risk of dying at the time of the adverse event or it is suspected that the use or continued use of the product would result in the patient's death; (3) hospitalization (initial or prolonged); (4) disability, i.e., resulted in a significant, persistent, or permanent change, impairment, damage or disruption in the patient's body function/structure, physical activities or quality of life; (5) congenital anomaly, i.e., there are suspicions that exposure to a medical product prior to conception or during pregnancy resulted in an adverse outcome in the child; (6) requires intervention to prevent permanent impairment or damage. Serious adverse events will be reported immediately to the Study PI, site PI and the local IRB. The PI will notify the DSMB.

The only indication for breaking the randomization code is when it is medically necessary to unmask the study drug assignment to be able to treat the patient, such as an allergic reaction or severe side effect that appears to be related to the medication.

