VCE offers potential advantages over traditional EGD including the ability to be performed 24 hours a day without sedation and interpreted at the bedside by emergency physicians. In addition, VCE is much less invasive, is painless, and enables the patient to pursue normal daily activities after the procedure. ED physicians may use the information to make real-time decisions regarding the need for hospitalization, endoscopic hemostasis, and risk stratification. Real-time imaging has been shown to be helpful in early diagnosis of bleeding lesions [1], and the videos generated can be sent to an off-site specialist for an over-read after the initial ED interpretation. This workflow is similar to that of many current ED diagnostic tests such as electrocardiograms and radiology examinations. This ability to transmit images could become especially important in rural communities or in communities that have limited access to a gastroenterologist. Incorporation of VCE into ED practice could follow a trajectory similar to that of point-of-care ultrasonography, an imaging modality in which ED physicians have become increasingly skilled and for which indications continue to expand [2].

In patients requiring VCE, most contraindications are relative and the procedure has been performed safely in a variety of clinical settings [3]. Pacemakers and other electrical medical

devices are not a contra- indication to the procedure with newer versions of the capsules. The only absolute contraindications are bowel obstruction and pregnancy [4]. There is a low risk of non-natural excretion of the capsule estimated at less than 1 in 100 [5]. In general, the procedure poses significantly less risk than traditional EGD, and multiple studies have shown that VCE is well tolerated in ED patients with suspected acute UGIB [6-8].

The American Society of Gastrointestinal Endoscopy states that credentials for VCE should be determined independently from other endoscopic procedures such as colonoscopy, sigmoidoscopy, or any other endoscopic procedure [9]. The American Society of Gastrointestinal Endoscopy emphasizes sound medical training, appropriate patient selection, correct interpretation, and continued medical management for all patients. VCE requires only image interpretation and does not require procedural skill training associated with other endoscopic procedures; therefore, ED physicians can meet these criteria with basic training.

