### **2.3.3 Discussion**

The typical primary care, urgent care or emergency care provider is unable to evaluate common and serious conditions of the gastrointestinal tract such as a bleeding peptic ulcer. As such, more than 80% of patients who present to US ED's with suspected bleeding in their upper GI tract require hospitalization, procedural sedation by an anesthesiologist, and a traditional tube-based upper endoscopy by a gastroenterologist. While this traditional process is safe and effective, it is not efficient for low-risk patients and not timely for all high-risk patients. The opportunity to bring VCE to the front-lines of US medical care will revolutionize how we manage upper GI bleeding and shed light on critical diseases that have heretofore been hidden from providers. This trial is an important step toward demonstrating that VCE is a safe and effective tool to risk-stratify upper GI bleeding and improve quality of emergency care for all patients.

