### **11.3 Final Analysis Plan**

The analysis will be conducted in several stages. First, we will compare the baseline characteristics of the two study groups to determine if randomization was successful. We will also compare the baseline characteristics of the study samples by enrollment site. Second, we will compare the VCE and EGD results and classify all study subjects according to whether there is a high versus low risk lesion present. The VCE and EGD results may differ because they are not being performed at the same time and GI bleeds can resolve or change so it is unlikely that there will be perfect agreement between the two modalities. In cases where one modality identifies a low risk lesion and the other one a high-risk lesion, we will classify the lesion as high risk. If the VCE could not adequately visualize the tract, we will classify the results according to the EGD. We will compare the sensitivity and specificity of VCE and EGD for identifying high risk lesions. Finally, we will separately compare the admission rates of high-risk lesions and low risk lesions between the two study groups. We will compare admission rates aggregated across the four study centers as well as within each study center.

For tertiary outcomes, we will compare the outcomes by study group using a chi-square test statistic if the outcome is categorical such as the presence of an adverse event and a t test (normally distributed) or median test (non-normally distributed) if the outcome is continuous such as hospital or ED length of stay.

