### 18.14 Adverse Event Form

## Adverse Event Form

Initials of person completing form \_\_\_\_\_

Start Date/Time \_\_\_\_\_

Stop Date/Time \_\_\_\_\_

During PillCam Administration Yes No

Post PillCam Administration Yes No

Please describe the AE \_\_\_\_\_

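### Adverse-event questions and timing boxes centre on the capsule, with no item for sedation or hospital-stay harm, yet adverse events are compared by arm

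*Combined protocol and SAP*

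**What the plan says.** **Prompt list.** Section 7.6 has patients asked, at all contacts, about a fixed list: "patients will be questioned regarding side effects or symptoms associated with the study medication which are as follows". The six items are trouble swallowing the capsule, a stuck capsule, failure to pass it, surgery, aspiration and sensor-related skin irritation. The same section gives other sources too: "Results of clinical observations, laboratory tests, and reported events form the basis for evaluating the safety profile of this therapy".

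**Forms.** The adverse event form (18.14) has start and stop date/time, then two timing boxes: "During PillCam Administration Yes No" and its post-administration counterpart. It grades relationship to the study protocol/procedures and, separately, to the PillCam. Section 8.9 has the form completed when a patient reports an event. The Day 7/30 call (18.12) covers bleeding symptoms, loss of consciousness, endoscopy and its results, return visits and readmission for bleeding. Chart review (18.13) covers transfusion, further endoscopy, hemostatic therapy, surgery and disposition.

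**Analysis.** Section 11.3 compares tertiary outcomes by study group, using a "chi-square test statistic if the outcome is categorical such as the presence of an adverse event".

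**Exposure.** Under 4.4, only CERA patients receive the capsule and the pro-motility drug. All control patients are to be admitted and have inpatient EGD. Discharged CERA patients are scheduled for outpatient EGD, and admitted CERA patients are expected to have inpatient EGD.

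**The concern.** A between-arm comparison of adverse events is fair only if both arms are asked about harm in the same way. Here the standing list concentrates on what the capsule can do. The harms of a hospital stay, which falls on every control patient and only some CERA patients, have no question of their own. They enter the data if a patient volunteers them, if staff notice them, or if they happen to match a chart-review item.

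Section 2.3.3 describes the usual pathway as hospitalization with "procedural sedation by an anesthesiologist, and a traditional tube-based upper endoscopy by a gastroenterologist", so admission and sedation are part of what the trial sets beside the capsule strategy. The stated goal (3.1) is safe discharge. A reader of the results will look at the adverse-event comparison for support, and a difference in either direction could reflect how events were sought rather than how often they happened.

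**Working it through.** No figure in the plan bears on this point, so the check is mainly a comparison of passages.

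**1. The six items in 7.6 against exposure in 4.4**

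| Item | Possible in control? |
|---|---|
| Difficulty swallowing the capsule | No |
| Capsule stuck | No |
| Capsule not passed | No |
| "Possible skin irritation from the sensors" | No |
| "Surgical intervention" | Yes, as worded |
| Aspiration | Yes, as worded |

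Four of six are CERA-only and two can occur in either arm. None names EGD, sedation or the hospital stay.

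**2. Whether another form fills the gap**

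- *Day 7/30 call (18.12).* The new-problem option and its free text sit under the question on endoscopy results, so they ask for a finding. They can catch a complication but do not ask for one. The form does not carry the 7.6 list, so how that list is administered and recorded is also unclear.
- *Satisfaction form (18.11).* It has a general question on any issues, but the form concerns the pill camera, and 4.4 step 9 assesses satisfaction in the experimental group.
- *Chart review (18.13).* No item for sedation events or hospital-acquired complications.
- *Adverse event form (18.14).* It can take any event, but 8.9 ties its completion to a patient report, and the timing boxes have no meaning for a control patient.

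**3. Which gaps differ by arm**

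- *EGD and sedation harm:* EGD is planned in both arms, so weak capture affects both.
- *Hospital-stay harm:* 100% of controls are assumed admitted (3.2.1). Admitted CERA patients share the gap; discharged CERA patients have no inpatient stay. This is the main arm-related gap.
- *Pro-motility drug reactions:* given in CERA only, named as a minor adverse event in 2.3.1, absent from the 7.6 list. This gap lowers the CERA count.
- *Initial hospitalization as a serious event (7.6, 10.2):* no exception is made for the planned control admission. Read literally, every control patient could count, against only the admitted CERA patients.

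The first two listed mechanisms that differ by arm (capsule prompts, hospital-stay harm) raise the CERA count relative to control; the last two do the reverse.

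**4. Illustration of size**

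Assumptions, not from the documents: 50 per arm (N = 100 is stated, the allocation ratio is not), equal true event rate *r* in both arms, full capture in one arm and capture share *c* in the other, two-sided 0.05.

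Error in the observed difference = *r* × (1 − *c*). With *c* = 0.5:

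| *r* | Observed rates | Error | P(p<0.05), uncorrected chi-square | P(p<0.05), Fisher |
|---|---|---|---|---|
| 5% | 5% v 2.5% | 0.05 × 0.5 = 2.5 points | 0.08 | 0.01 |
| 10% | 10% v 5% | 0.10 × 0.5 = 5 points | 0.15 | 0.06 |
| 20% | 20% v 10% | 0.20 × 0.5 = 10 points | 0.30 | 0.20 |

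Probabilities are sums of the two binomial distributions over all tables with p<0.05. With full capture in both arms, the chi-square figure is 0.04 to 0.05 across these rates. The table is symmetric: it applies whichever arm is under-captured.

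**The case against.** **Other routes exist.** Section 7.6 also relies on clinical observation, laboratory tests and reported events. The adverse event form records start and stop times and relationship to protocol/procedures, and serious events are reportable in either group (10.2). This stands, and it rules out the inference that control-pathway harms are never asked about. It does not make the questioning equal: the remaining routes depend on volunteering or incidental capture.

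**EGD is not a control-only exposure.** This also stands. The strategy avoids admission, not EGD, so under-capture of EGD or sedation harm is not specific to control. A reader might take the background statement that "the procedure poses significantly less risk than traditional EGD" as a premise the trial should test. It is background, not one of the objectives (3.1) or hypotheses (11.1), and with EGD planned in both arms no form change would let the trial test it.

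**Bias against the capsule.** A reader might infer that the comparison must be biased against VCE. The documents do not support a net direction: unprompted pro-motility reactions and a literal reading of the hospitalization criterion both work in its favour. Nor would adding assumed capsule complaints to the CERA rate and computing the chance of significance measure a bias. Those complaints are real harms of the strategy, so that is power to detect a true excess.

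**It is a tertiary comparison.** True. Section 3.2 names mortality, re-bleeding, transfusion and surgery, which are collected in both arms and do not rest on the prompt list, and it already sets capsule-specific events apart as a category. The point is confined to the any-event comparison and to minor events in particular.

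**Conclusion.** The concern holds in a limited form. The 7.6 list and the 18.14 timing boxes are built around the capsule, no form has a dedicated item for sedation or hospital-acquired harm, and 11.3 nevertheless tests presence of an adverse event by arm. Minor events are solicited unequally, so that test cannot be read fairly. The main arm-related gap is hospital-stay harm.

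The size cannot be taken from the documents. Under the assumptions stated, missing half the events in one arm puts the observed difference out by 2.5 to 10 points for true rates of 5% to 20%, and raises the false-positive chance of the chi-square test from about 0.05 to between 0.08 and 0.30. The direction is uncertain. The primary outcome and the named major safety outcomes are unaffected by the prompt list, though how a planned admission enters the serious-event count needs stating.

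**What to change.** 1. **7.6 and 18.12:** use one arm-neutral question list in both arms at Day 7 and Day 30: any problem during or after endoscopy or its sedation, any reaction to study-related medication, and any new problem that began in hospital, each with dates.
2. **18.14:** replace the two PillCam timing boxes with timing relative to randomisation, using the start date/time already recorded. Add attribution to EGD/sedation and to the hospital stay beside the existing protocol/procedures and PillCam items.
3. **11.3:** report capsule-specific events separately, as a CERA rate with an exact confidence interval. Restrict the between-arm test to events elicited in the same way in both arms.
4. **11.3, with a cross-reference from 7.6 and 10.2:** state that the protocol-planned index admission is not itself counted as a serious adverse event in the comparison.

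The cost is a form revision and two or three more questions on calls already scheduled. The downside is a slightly longer call and more minor events to record. For patients already followed up under the current forms, the new items would be missing, so the analysis should say which patients were asked which questions.

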## **8 QUESTIONNAIRE ADMINISTRATION**

Data will be collected on standardized forms on which nearly all responses have been pre-coded. Each form is briefly described below:

### **8.1 Cheer 1: Screening Log**

Screening Log lists all patients screened for the study and some demographic data.

### **8.2 Cheer 2: Eligibility and Randomization Form**

Eligibility and randomization form will collect the specific inclusion and exclusion criteria for study consent and participation.

Affix randomization label on this form.

### **8.3 Cheer 3: Patient Data Collection Form**

Patient data collection form is completed for all randomized patients. This form includes detailed medical data obtained during screening for the study.

### **8.4 Cheer 4: Video Capsule Endoscopy Data Collection sheet**

This form is completed by the Gastroenterologist completed the VCE read.

### **8.5 Cheer 5: EGD Data Collection Sheet**

This form is completed by the Gastroenterologist completing the EGD read Interpretation Form.

### **8.6 Cheer 6: Patient Satisfaction**

This form is completed during the day 7 and day 30 follow up contact.

### **8.7 Cheer 7: Patient Follow up**

This form is completed during the day 7 and day 30 follow up contact, please verify information via EHR if necessary.

### **8.8 Cheer 8: Hospitalization Course/ Chart Review**

This form collects information on the hospitalization and procedures during the patient's hospital stay.

**8.9      Cheer 9: Adverse Event Form/ Serious Event  
From**

This form is completed if patient reports any AE or SAE's. Report to PI within 24 hours, SAE's are reported immediately.

**8.10:      Cheer 10: Protocol Deviation**

This form is completed if there is a deviation from the protocol at any time during the patient's course of participating in the study.

## **9 WEB DATA ENTRY SYSTEM**

For this protocol, web data entry screens corresponding to the study forms listed above will be developed and maintained by GWU. Clinical center staff will enter data into the RedCap database for de-identified data. GWU is no longer able to maintain identifying information in RedCap.

Each site will maintain their own record keeping for maintaining their source documentation for patient information pertaining to follow up contact and file collection of physical source documentation. Please follow your institutional IRB for record maintenance.

## **10 ASSESSMENT OF SAFETY**

### **10.1 Unanticipated Problems**

#### ***10.1.1 Capsule Retention, Capsule Retention, Group Crossover***

### **10.2 Serious Adverse Events**

Serious adverse events will be reported immediately to the Study PI and the local IRB. Additional procedures are warranted for cases of serious adverse events which is defined by the FDA as a patient outcome that is:

- (1) Death;
- (2) Life-threatening, i.e., the patient was at substantial risk of dying at the time of the adverse event or it is suspected that the use or continued use of the product would result in the patient's death;
- (3) Hospitalization (initial or prolonged);
- (4) Disability, i.e., resulted in a significant, persistent, or permanent change, impairment, damage or disruption in the patient's body function/structure, physical activities or quality of life;
- (5) Congenital anomaly, i.e., there are suspicions that exposure to a medical product prior to conception or during pregnancy resulted in an adverse outcome in the child;
- (6) Requires intervention to prevent permanent impairment or damage.

If a patient in either group experiences any of the aforementioned six outcomes that may be possibly related to the research protocol, including but not limited to the following categories of risk:

- (1) Missed gastrointestinal lesion;
- (2) Capsule ingestion;
- (3) Capsule retention;
- (4) Delayed definitive care;

### **10.3 Reporting Procedures**

All adverse events get reported to site IRB, to study PI and DSMB.

## **11 HYPOTHESIS AND ANALYSIS**

### **11.1 Study Hypotheses**

We hypothesize that there will be no significant difference in the hospital admission rate among subjects diagnosed with a high-risk lesion between the two study groups whereas there will be a significant difference in the hospital admission rate among subjects with a low risk lesion.

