**4.4 Study procedure:**

1. Screen potential patients with signs of upper GI bleeding (melena, h/o hematemesis or coffee-ground emesis) from general pool of ED patients. (Form used, *CHEER:1*)
2. Patients who screen as eligible will be approached about potential interest, to review of inclusion and exclusion criteria, and obtain informed consent. (*See below for full list of inclusion/ exclusion criteria.*)
3. Research Coordinator will calculate traditional risk stratification scores (Glasgow – Blatchford and Rockall).
4. All consented patients will be given a study ID and recorded in enrollment log. (Form used, *CHEER:2*)
5. Once enrolled, all subjects will be randomized to either Active Control (AC) [admission plus EGD within hospital stay] or experimental Capsule Endoscopy Risk Assessment (CERA) in ED.
6. Only patients randomized to the experimental arm will receive video capsule endoscopy in the emergency department. 20 to 60 minutes before capsule ingestion, each patient in the experimental arm receives a single dose of intravenous metoclopramide 10 mg (or erythromycin 500mg intravenously if there is a contraindication), which helps to promote gastric motility and improves visualization of the gastric mucosa at endoscopy. The Research Coordinator (RC) will prepare the patient for VCE. (*See below for description of procedure.*)
7. Within 2 hours of presenting to the ED, patient will ingest video capsule-- RC will monitor progress on real-time viewer for passage through pylorus. Upon passing the pylorus, we will record 5 more minutes of video or until battery runs out – whichever occurs first.
8. Patient data will be completed using a standardized data collection tool including the following elements: chief complaint of patient, history of present illness, past medical history, pertinent lab findings, current medications, vital signs, focused physical exam findings and all relevant treatments administered during the ED and hospital stay. (Form Used, *CHEER:3*)

9. At completion of VCE, patient satisfaction regarding VCE will be assessed in patients in the experimental group. (Form used, *CHEER*: 4)
10. For Active Control (AC) group each patient will be admitted.

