During hospital admission, EGD will be performed on all subjects and hemostasis therapy applied as necessary. The study team decided against mandating that EGD be performed within 24 hours of hospital admission. This is a pragmatic trial. The longer the duration between the inpatient EGD and the ED VCE the greater the likelihood of discrepancy in the findings that may be due to a change in the lesion as part of its natural course or due to treatments delivered. However, the primary objective of the study is not to evaluate diagnostic accuracy of the ED VCE. The study team decided it was more important to enroll subjects in a timely manner than exclude subjects because the inpatient EGD was not completed within 24 hours.

For the experimental CERA group, subjects will be monitored for a minimum of 4 hours after ingestion. VCE will be undergo a formal review after completion of the VCE by a staff gastroenterologist with extensive experience in VCEs of the small bowel, colon, and esophagus. Both research personnel and the gastroenterologist will undergo a capsule training program organized by Medtronic and receive accreditation after the training.

11. Subjects in the experimental arm who have no sign of active bleeding, show no serious endoscopic findings on capsule, and have stable hemoglobin, blood pressure and heart rate for at least 4 hours will be discharged from the ED. Discharged CE patients will be scheduled to have an outpatient EGD within 3 days post discharge. Patients will be instructed to return to the ED sooner if signs of new bleeding develops. The Research Coordinator will facilitate setting up this appointment for the patient.

Any subject in the experimental arm with a positive VCE or a negative VCE but has a drop in Hemoglobin  $\geq 3$  at 4 hours or an elevated HR or low BP will be admitted. A hemoglobin drop between 2 and 3 will NOT automatically transfer patient to active control arm. In these cases, decision to proceed will be up to discretion of treating physician. We anticipate that all admitted patients in the experimental arm will undergo EGD in the hospital (same as AC arm.)

12. Primary Outcome: (1) Percent Discharged Home. Assumption is that 100% of Active Control / standard risk assessment will be admitted.
13. Secondary Outcome: Sensitivity and specificity of VCE compared to EGD

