### **11.2 Sample Size Considerations**

With 100 patients, we will have adequate power (i.e.  $\geq 80\%$ ) to detect a 25% difference or greater in admission rates for subjects with low risk lesions with p- value less than 0.05. We assume that the controls will a 100% admission rate. We anticipate 20% or less of all subjects to be diagnosed with a high-risk lesion, we are unlikely to have adequate power to detect a significant difference in the hospital admission rate between the two study groups.

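### Section 11.1 predicts a non-significant result for high-risk admissions, with no margin and admitted low power, so a null finding there could not show that high-risk patients are being admitted

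*Combined protocol and SAP*

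**What the plan says.** Section 11.1 states one hypothesis in two halves. For low-risk lesions it expects a significant difference in admission rate. For high-risk lesions it expects that "there will be no significant difference in the hospital admission rate among subjects diagnosed with a high-risk lesion between the two study groups".

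Section 11.2 sizes the trial on the low-risk half: 100 patients, a 25-point difference, at least 80% power, and every control admitted. On the other half it says "We anticipate 20% or less of all subjects to be diagnosed with a high-risk lesion" and then "we are unlikely to have adequate power to detect a significant difference in the hospital admission rate between the two study groups".

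Section 11.3 says "we will separately compare the admission rates of high-risk lesions and low risk lesions between the two study groups". It names no test for this comparison; chi-square appears only for tertiary outcomes. A patient counts as high-risk if either examination says so: where "one modality identifies a low risk lesion and the other one a high-risk lesion, we will classify the lesion as high risk". Section 4.4 adds that "Only patients randomized to the experimental arm will receive video capsule endoscopy in the emergency department".

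Section 3.2 makes percent discharged home the primary outcome and the sensitivity and specificity of capsule endoscopy (VCE) the secondary outcome. The high-risk admission comparison is neither.

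**The concern.** Failing to reject a null hypothesis is not evidence that two rates are alike, least of all where the plan itself expects too little power. Section 11.1 nevertheless makes the non-significant result the predicted finding, so that finding would naturally be read as support. Nothing in sections 11.1 to 11.3 says how large a difference would matter or how precise the estimate must be.

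This half of the hypothesis matters because the primary outcome cannot do its job. Percent discharged rises whether or not each discharge was appropriate. The high-risk half is where the stated hypotheses address whether patients with serious lesions are still admitted.

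The planned sensitivity estimate overlaps with this question but is a different quantity. Under section 4.4 a VCE-negative patient can still be admitted on haemoglobin, heart rate or blood pressure. Section 3.2 also allows inconclusive capsules. Section 11.3 states no confidence interval for sensitivity.

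**Working it through.** **Inputs.** From the plan: 100 subjects; at most 20% high-risk; 100% of controls admitted; p below 0.05 (all in section 11.2). Assumed, because not stated: 1:1 allocation and two-sided testing. The upper figure of 20 high-risk patients is used, first split evenly.

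**1. The plan's own figure.** With 80 low-risk patients, 40 per arm, 100% v 75% admitted (mean 0.875):

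z = [0.25√40 − 1.96√(2 × 0.875 × 0.125)] / √(0.75 × 0.25) = (1.581 − 0.917) / 0.433 = 1.53, so power is 93.8%.

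An exact calculation with Fisher's test (significant from 6 of 40 discharged) gives 95.7%. The claim of at least 80% for the low-risk half holds.

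**2. High-risk stratum, 10 v 10, with 0 control and 3 CERA patients sent home.**
- Fisher, two-sided: 2 × C(10,3)/C(20,3) = 2 × 120/1140 = 0.21.
- Uncorrected chi-square: 20 × (10 × 3 − 0 × 7)² / (10 × 10 × 17 × 3) = 18000/5100 = 3.53, p = 0.060.
- Yates: 20 × (30 − 10)² / 5100 = 1.57, p = 0.21.
- Clopper-Pearson 95% CI for 3/10: 6.7% to 65.2%.
- For 0/10 the upper limit is 1 − 0.025^(1/10) = 30.8%.

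The first significant count is 5 of 10 by Fisher (0.033) or Yates (0.039), and 4 of 10 by uncorrected chi-square (0.025).

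**3. Dependence on the split.** If the 20 high-risk patients fall at random over 50 + 50, the chance of exactly 10/10 is C(20,10) × C(80,40)/C(100,50) = 0.197.

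| Control/CERA | Sent home | Fisher | Yates | Uncorrected |
|---|---|---|---|---|
| 12/8 | 2 of 8 | 0.147 | 0.287 | 0.068 |
| 11/9 | 2 of 9 | 0.190 | 0.369 | 0.099 |
| 11/9 | 3 of 9 | 0.074 | 0.148 | 0.038 |
| 10/10 | 3 of 10 | 0.211 | 0.210 | 0.060 |
| 9/11 | 3 of 11 | 0.218 | 0.285 | 0.089 |
| 8/12 | 4 of 12 | 0.117 | 0.209 | 0.068 |

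**4. How often the result would be non-significant.** Take a true send-home rate of 28% among high-risk CERA patients. This is illustrative: it is 1 minus the 72% lower confidence limit for sensitivity cited in section 2.1, which covers only capsules that passed the pylorus. Sum the binomial probability of each non-significant count over the hypergeometric split:
- 20 high-risk in all: 82% (Fisher), 64% (uncorrected).
- 10 high-risk in all: 97% (Fisher), 89% (uncorrected).

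**The case against.** - *Section 11.1 is a prediction, not a decision rule, and section 11.2 discloses the low power.* Both are true. A reader might infer that the plan commits to declaring equivalence or safety from a null result. No passage says so, and that reading is not supported. What stands is narrower: the predicted finding is one that cannot support the claim it appears to make, and the disclosure supplies no other criterion.
- *Missed lesions are watched elsewhere.* Section 2.3.1 lists missed high-risk lesions and delayed definitive care among potential major adverse events. Section 3.2 collects serious adverse events at days 7 and 30, and section 10.2 names missed lesions as a risk category. A reader might infer that high-risk discharges go unmonitored; these sections show otherwise. They do not repair the hypothesis wording.
- *The example is fragile.* This stands. At 11/9, 3 of 9 is significant by uncorrected chi-square, and at 10/10 that test is already close to 0.05. It would be wrong to say that 3 in 10 always escapes detection.
- *The test does discriminate.* This stands in part. At a 5% send-home rate the result is non-significant 99.9% (Fisher) or 99.3% (uncorrected) of the time, against 82% or 64% at 28%. By uncorrected chi-square that is weak discrimination, not none.
- *The averaged figures assume a symmetric split and a send-home rate of 1 minus sensitivity.* This stands. The either-modality rule can add VCE-positive/EGD-negative patients to the CERA stratum only, and they are due for admission. Inconclusive capsules lie outside the model. The figures are therefore illustrative and are not a bound in either direction.

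**Conclusion.** The point holds as one of interpretation and should be fixed. With about 20 high-risk patients or fewer, a non-significant admission comparison cannot show that high-risk patients in the CERA arm are being admitted. At an even split, 3 of 10 sent home is non-significant by all three tests calculated, and 0 of 10 still leaves 31% inside the interval. If 28% were sent home, the predicted result would still appear about 82% of the time by Fisher and 64% by uncorrected chi-square.

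These sizes rest on 1:1 allocation, two-sided 0.05, all controls admitted, the upper figure of 20% high-risk and a symmetric split. They shift with the split and with the test, which the plan does not name. The absence of a margin or interval criterion, and the admitted low power, depend on none of these assumptions.

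A reader might go further and infer that the trial's main result is compromised. The documents do not support that: the primary outcome and the low-risk comparison are unaffected, and the low-risk power statement reproduces.

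**What to change.** In sections 11.1 and 11.3, replace the no-difference hypothesis for the high-risk stratum with estimation: the proportion of high-risk CERA patients discharged from the ED, with an exact 95% CI. Add one sentence saying that non-significance will not be read as equivalence or safety.

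Optionally, report the same proportion with an EGD-defined denominator as a sensitivity analysis, because only one arm has VCE findings feeding the either-modality rule. That version has its own weaknesses. The plan notes of the two examinations that "they are not being performed at the same time and GI bleeds can resolve or change", and also that "The study team decided against mandating that EGD be performed within 24 hours of hospital admission", so some lesions may have resolved before EGD. It also loses patients who have no EGD.

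The findings and disposition needed are already planned for collection, and the primary outcome does not change. The costs are a wide interval in place of a p-value, and a protocol amendment with IRB approval (section 15.2). The document carries the date 9/27/19 and section 6.2 schedules recruitment to April 2019, so the amendment should be dated and should say whether outcome data had been seen.
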